1 SYNOPSIS

Title	A Phase 2 Randomized, Double Blinded, Placebo Controlled Study of Oral Favipiravir Compared to Current Standard of Care in Subjects with Mild or Asymptomatic COVID-19
Design	
This is a Phase 2 Double Blinded, Placebo Controlled Study evaluating the efficacy, safety and pharmacokinetics of favipiravir in adult subjects with PCR-positive, mild or asymptomatic COVID-19 infections. The study is a multicenter trial that will be conducted in up to 5 sites nationwide.
 
Subjects will be randomized to receive either favipiravir + current Standard of Care (SOC) or placebo + SOC.
 
For those subjects in the favipiravir + SOC arm, the dose regimen will be 1800 mg BID favipiravir on the first dose (day 1) followed by 800 mg BID for the next 9 days (days 2-10).
 
NOTE: 600 mg BID for subjects with Child-Pugh A liver impairment on days 2-10.
 
Subjects in the SOC arm will receive placebo.
 
The total anticipated duration of the study for each patient is 28 days.

Objectives	
Primary Objective
 
To evaluate the efficacy of oral favipiravir plus SOC compared with placebo plus SOC in reducing the duration of shedding of SARS-CoV2 virus in patients with mild or asymptomatic COVID-19.
 
Secondary Objectives
 
 1. To evaluate the efficacy of oral favipiravir compared with placebo in reducing the onset or duration of symptoms, hospitalizations, or ED visits in patients with mild or asymptomatic COVID-19. 2. To assess the safety and tolerability of favipiravir in this subject population. 3. To assess the development of antibodies against SARS-CoV-2 4. To evaluate any changes in the PK profile of favipiravir and its major metabolite M1 in this subject population
Endpoints	
Primary Endpoint:
 
Time until cessation of shedding of SARS-CoV-2 virus, defined as the time in days from randomization to the first of two consecutive negative RT-PCR results of self-collected nasal swabs.
 
Secondary Endpoints
 
 1. Nucleic acid (RT-PCR) from oropharyngeal swabs collected on Days 1, 5, 10, and 28

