8 EFFICACY, PHARMACOKINETICS AND SAFETY ASSESSMENTS

8.1 Efficacy Assessments

Primary Measurement (Efficacy):

1. Nasal swab for PCR taken daily from Day 1 to Day 10, and Days 14, 21, and 28.

Secondary Measurements (Efficacy):

1. Nucleic acid (RT-PCR) from oropharyngeal swabs collected on Days 1, 5, 10, and 28.
2. Symptom improvement or worsening: Subjects will fill in a diary daily, recording the following symptoms:
 - a. Cough/Shortness of breath/dyspnea
 - b. Fatigue
 - c. Headache/Body aches
 - d. Joint pain
 - e. Chest pressure
 - f. GI symptoms including nausea, vomiting, and/or diarrhea
 - g. Abdominal pain
 - h. Sore throat
 - i. Nasal congestion
 - j. Chills
 - k. Runny nose
 - l. Oral temperature taken after 4 pm and at least four hours after ingesting the most recent antipyretic (acetaminophen or NSAID)
 - m.
 - n. New loss of taste or smell
 - o. Abdominal pain
 - p. Rash
3. Blood for determination of antibodies to SARS-CoV-2 will be obtained on Days 1, 14, and 28.
4. Number of subject hospitalizations, emergency department visits, incidence of respiratory failure, deaths, and proportions of subjects alive, not hospitalized, and free of respiratory failure on day 28

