9 STATISTICAL METHODS

Complete details of all statistical analyses, including methods for handling missing data, will be included in a formal statistical analysis plan (SAP), to be completed as soon as possible after study initiation.

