The number of hospitalizations, emergency department visits, incidence of respiratory failure, deaths, and proportions of subjects alive, not hospitalized, and free of respiratory failure will be estimated for each arm, with 95% confidence intervals. Respiratory failure is defined as the need for mechanical ventilation, ECMO, non-invasive ventilation, or high-flow oxygen

Our analyses will use multiple imputation methods that assume data are missing at random by including all baseline characteristics, treatment assignment, and reasons for missingness in the imputation model. This approach will be applied to any analysis involving endpoints or key variables where any missing data occurs in order to adhere to the ITT principle. Assumptions regarding missingness will be addressed in sensitivity analyses.

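### The imputation model names no post-baseline swab result, so if applied as written it can contradict a participant's own swabs and slightly inflate the primary hazard ratio

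*Combined protocol and SAP*

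**What the plan says.** Section 9.6 of the combined protocol and SAP states: "Our analyses will use multiple imputation methods that assume data are missing at random". It supports that assumption by "including all baseline characteristics, treatment assignment, and reasons for missingness in the imputation model". The scope is wide: "This approach will be applied to any analysis involving endpoints or key variables where any missing data occurs". The same paragraph adds that "Assumptions regarding missingness will be addressed in sensitivity analyses", without details.

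The Synopsis counts the primary endpoint from randomization to "the first of two consecutive negative RT-PCR results of self-collected nasal swabs". Section 8.1 gives the schedule: "Nasal swab for PCR taken daily from Day 1 to Day 10, and Days 14, 21, and 28", which is 13 swabs. It also lists oropharyngeal RT-PCR on Days 1, 5, 10 and 28.

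Section 9 defers the details: "Complete details of all statistical analyses, including methods for handling missing data, will be included in a formal statistical analysis plan (SAP"). No section adds swab results to the imputation model or says whether a single swab or a derived event time is imputed.

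**The concern.** For a swab missing on a given day, the best predictors are the same participant's results just before and after it. None of the three named items supplies them, except that the Day 1 result might count as a baseline characteristic. A model with only arm and baseline variables pulls each imputed swab toward its arm's average for that day. A gap inside a run of positives can then be filled with negatives, and a gap inside a run of negatives can be filled with a positive.

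Because the event needs two negatives in a row, such values can bring it forward or push it back. If favipiravir works, false early clearance is likelier on favipiravir and false delay is likelier on placebo, so both errors enlarge the apparent effect. Gaps are foreseeable, since participants collect and mail the swabs themselves (Section 5.1).

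The third item has its own difficulty. A reason for missingness is recorded only where the value is absent, so the observed results cannot show how reason and value are related.

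**Working it through.** The documents give no missing-swab rate, number of imputations or imputed result, so there is no plan figure to reproduce. The check asks what the listed variables would do if used alone.

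**Inputs from the documents.** Medians of 14 days (control) and 7 days (treatment) and 60 per arm (Section 9.2); 13 swab days (Section 8.1); the two-consecutive-negative rule (Synopsis).

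**Assumptions not in the documents.** Exponential clearance times; 5% to 20% of swabs missing at random; swab-level imputation; no prognostic baseline covariates; no positive after clearance unless stated.

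**Step 1: chance of a contradictory value.** With arm as the only informative predictor, P(negative on day d) = 1 − 0.5^(d/median).

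- Day 5 swab between two positives, filled negative: control 1 − 0.5^(5/14) = 0.22; treatment 1 − 0.5^(5/7) = 0.39.
- Day 5 swab between two negatives, filled positive: control 1 − 0.22 = 0.78; treatment 1 − 0.39 = 0.61.
- Days 7 and 8 both missing between positives, both filled negative (a false event): control 0.29 × 0.33 = 0.10; treatment 0.50 × 0.55 = 0.27.
- Day 9 positive, Days 10, 21 and 28 negative, Day 14 missing: a positive drawn on Day 14 moves the event from Day 10 to Day 21. Its probability is 0.5^(14/14) = 0.50 in control and 0.5^(14/7) = 0.25 in treatment.

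**Step 2: effect on the primary estimate.** Simulated trials drew missing swabs from arm-by-day rates. The shift compares the same trial with and without missing swabs.

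| Missing swabs | Shift in log HR | exp(shift) | A true HR of 2.00 reads as |
|---|---|---|---|
| 5% | +0.012 | 1.012 | 2.02 |
| 10% | +0.024 | 1.024 | 2.05 |
| 20% | +0.048 | 1.049 | 2.10 |

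Standard errors of the shifts are 0.002 to 0.004. At 20% missing the SD of the log HR was 0.233, against 0.206 without this imputation. The variance ratio is (0.233/0.206)² = 1.28. With both medians at 14 days there was no shift, and rejection stayed at 4% to 6%.

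**Step 3: does using the participant's own swabs remove it?** A separate set of 300 trials gave shifts of +0.010, +0.023 and +0.046. In those trials 17%, 32% and 53% of participants had at least one imputed swab that contradicted their own results. Drawing the clearance time within the participant's own bracketing swabs moved the log HR by at most 0.001.

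A less idealized version (200 trials, 5% dropout) added the previous and next swab to a chained imputation model. Where the two neighbours agree, contradictions fell from about 38% to 2–3%. Participants whose event time or status was altered fell from 13.5% to 9.8% at 10% missing, and from 24.6% to 17.9% at 20%.

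With 5% of swabs misread and 20% missing, the advantage is less clear. Mean HR was 1.91 with complete data, 1.97 with the listed variables and 1.86 with adjacent swabs (Monte Carlo error about 0.03 each). Altered event times or statuses fell only from 27.0% to 23.0%.

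**The case against.** The strongest reply is that Section 9.6 is a summary. Its wording does not make the list exhaustive, it does not mention swabs or the level of imputation, and Section 9 leaves missing-data methods to a later SAP. Imputation of repeated measures normally uses the other observed measurements. If only event times after dropout were imputed, no swab lying between observed results would be overwritten. All of this stands. A reader might infer that the plan excludes the participant's swabs and will produce contradictory results; the documents do not say so. What remains is that the list is offered as the support for missing at random, covers the primary endpoint, and is nowhere supplemented. Imputing the event time from the same list would not cure the problem either: unless the draw is restricted by the observed series, it could fall before the last observed positive. That variant was not simulated.

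A reader might also infer that one false negative between two positives creates an event. It does not, because two consecutive negatives are needed. Longer gaps, and false positives among negatives, are what move the date.

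The effect is small. At 10% missing, 0.024/0.206 is about 0.12 of one SD of the log HR. The simulations also use a weaker model than the one listed, since prognostic baseline covariates would reduce contradictions somewhat. They use 60 per arm, whereas Section 9.4 analyses everyone randomized (180, with 33% assumed negative on Day 1). These limits apply to the figures and leave the mechanism intact.

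**Conclusion.** The point holds conditionally. If missing swabs are imputed from the listed variables as written, imputed values can contradict adjacent observed swabs. Under the plan's medians and random missingness, the log HR is then inflated by about 0.01 at 5% missing, 0.02 at 10% and 0.05 at 20%, with a larger SD (about 0.23 against 0.21 at 20%).

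A stronger reading, that the primary test becomes invalid, is not supported. No shift and no type I error inflation were seen under the null, although runs of this size cannot exclude a change of a percentage point or so. Larger effects would need missing rates for which the documents give no basis. The benefit of conditioning on own swabs is clearest when positives do not recur after clearance, and smaller when swabs are misread. The point about reasons for missingness needs no simulation: it follows from when a reason is recorded.

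**What to change.** In the SAP, before unblinding:

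1. State whether single swabs or the derived event time are imputed.
2. For the shedding endpoint, condition the imputation on the participant's observed nasal and oropharyngeal PCR series as well as arm and baseline covariates. Alternatively, derive the event from the available results and analyse it as interval-censored. Either way, say how a positive after a negative is handled.
3. Use reasons for missingness to define the promised sensitivity analyses, and drop them as a predictor.
4. Keep the planned imputation for missing baseline covariates.

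The cost is SAP wording and modest extra programming. Trial conduct, visits and data collection do not change. Cheap improvement.

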9.7 Safety Analysis

The frequency of adverse events and serious adverse events will be tabulated by type and by treatment arm. AEs will be compared by arm using the Chi-squared test or Fisher's exact test, as appropriate, in the safety analysis set.

The original exact terms in the electronic data capture (EDC) system used by Investigators to identify AEs other than symptoms of COVID-19 will be fully described and coded according to the Medical Dictionary for Regulatory Activities (MedDRA). Treatment-emergent AEs will be defined as those occurring coincident with start of treatment and through 28 days post-treatment. TEAEs will be summarized overall and by treatment group and by MedDRA body organ system and preferred term, severity, relatedness, and seriousness.

An overall summary of TEAEs will be presented by treatment, with subject counts and percentages of subjects with the event. This summary will include subjects with any TEAE, any treatment-related TEAE, any serious TEAE, any treatment-related serious TEAE, TEAEs leading to study infusion discontinuation, treatment-related TEAEs leading to study infusion discontinuation, TEAEs leading to death, and treatment-related TEAEs leading to death. The difference in proportions between treatment groups in each of these categories will be calculated.

Summaries of changes over time in laboratory parameters, as well as counts and percentages of laboratory parameters that are Low, Normal, and High compared to the reference ranges will be presented by treatment at each visit and time point. Shift tables will be presented for laboratory parameters with defined severity grades.

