	
 2. Clinical worsening of COVID-19 in symptomatic subjects (clinical worsening defined the development of respiratory distress or symptoms that require hospitalization) or development of COVID-19 symptoms in asymptomatic subjects 3. Adverse events AEs and clinical laboratory tests for systemic safety including hematology and clinical chemistry 4. Development of antibodies to SARS-CoV-2 5. Time until cessation of symptoms (cessation of symptoms defined as absence of symptoms for at least 24 hours for those with mild symptoms). 6. Absence of development of any symptoms among those enrolled with asymptomatic infection. 7. Population PK analysis of favipiravir with assessment of maximum plasma concentration (C_{max}) and minimum plasma concentration (C_{min}) on Days 1, 5 and 10
Study Sites	Stanford University School of Medicine
Planned Enrollment	180 (90 in the favipiravir + SOC group and 90 in the placebo + SOC group)
Study Population	Adults with confirmed SARS-CoV-2 who are asymptomatic or experiencing mild to moderate symptoms
Subject Entry Criteria	
Inclusion Criteria (all questions must be answered YES)
 
 1. Adults (18-80) 2. Diagnosis of COVID-19 disease: 
 a. If symptomatic, but without signs of respiratory distress (as defined by SpO2 \leq94% on room air, RR \geq24, HR \geq110), with FDA-cleared molecular diagnostic assay positive for SARS-CoV-2 within 72 hours from initial swab to the time of commencing informed consent: Mild disease is defined as having at least 1 of the following: 
 i. Fever ($>98.7F$) b. Cough/Shortness of breath/dyspnea c. Fatigue d. Headache/Body aches e. Joint pain f. Chest pressure g. GI symptoms including nausea, vomiting, and/or diarrhea h. Abdominal pain i. Sore throat j. Nasal congestion k. Chills l. Runny nose

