2.3 Clinical Experience

Overall, more than 40 clinical studies with favipiravir have been conducted globally, mainly in the US and Japan. Recently, China has begun studying favipiravir in patients with severe influenza as well as COVID-19. More than 3100 study subjects have received at least one dose of favipiravir manufactured by Toyama Chemical. Favipiravir has been well tolerated in studies in adults and elderly subjects with uncomplicated influenza. A consistent safety profile composed of relatively low frequencies of mild to moderate adverse events (AEs) clustering around the system organ classes of gastrointestinal disorders, investigations, and infections and infestations has been characterized. Mild to moderate transient, asymptomatic elevations in serum uric acid and mild to moderate diarrhea are the two most common AEs known to occur with favipiravir. In double blind studies, the adverse event profile of favipiravir and placebo were similar with the exception of elevations of uric acid. Details can be found in the Investigator’s Brochure.

Favipiravir has been used in an open label study in patients with Ebola, (2400 mg twice eight hours apart, followed by 1200 mg 8 hours later and then 1200 mg BID for the following 9-13 days). Although conclusions about efficacy cannot be reached because of the lack of a concurrent control group, favipiravir at this regimen appeared to be well tolerated. A study in Japan in patients with Severe Fever with Thrombocytopenia administered 1800 mg BID Day 1 followed by 800 mg BID for the next 13 days. It has also been used under compassionate use in patients with rabies or other unusual RNA virus illnesses

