8.4.2 Definition of an Adverse Event

The FDA Safety Guidance, referencing 21CFR312.32(a), defines an Adverse Event as follows:

Adverse event means any untoward medical occurrence associated with the use of a drug in humans, whether or not considered drug related.

An adverse event (also referred to as an adverse experience) can be any unfavorable and unintended sign (e.g., an abnormal laboratory finding), symptom, or disease temporally associated with the use of a drug and does not imply any judgment about causality. An adverse event can arise with any use of the drug (e.g., off-label use, use in combination with another drug) and with any route of administration, formulation, or dose, including an overdose.

Adverse Events are **NOT**:

- **Clinical events related to the progression of COVID-19.**
- Medical or surgical procedures (e.g., surgery, endoscopy, tooth extraction, transfusion). The condition that leads to the procedure is the AE.
- Situations where an untoward medical occurrence has not occurred (e.g., hospitalization for elective surgery, social and/or convenience admissions).

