9.6 Efficacy Endpoint Analysis

Descriptive analyses

Descriptive statistics (proportions for categorical variables, means, medians, standard deviations, and interquartile ranges for continuous variables) will be reported for all key patient variables, including baseline and demographic characteristics, use of medications, compliance, and study completion status. Data that are missing on key patient characteristics and the outcome will be fully described, including any patterns of missingness (i.e., any relationships between missingness of a variable and patient characteristics).

A CONSORT diagram displaying the number of patients screened, eligible, and consented along with reasons for ineligibility will be provided. Graphical tools such as histograms, boxplots, and scatterplots will be created to assess quality of data and to display patterns over time.

Primary efficacy analysis

Time until shedding cessation will be compared between the two treatment arms using a Cox proportional hazards model adjusted for age and sex and stratified by site. The test will be performed at the $\alpha = 0.05$ level of significance. The hazard ratio for shedding cessation will be estimated, along with its 95% confidence interval, from a Cox proportional hazards model. If the proportional hazards assumption is not met, we will consider an extended Cox model that relaxes the proportional hazards assumption.

The distribution of shedding cessation will be estimated using the Kaplan-Meier method, and Kaplan-Meier curves will be presented for each treatment arm. Time to shedding cessation at the end of the study period along with 95% confidence intervals will be presented for each treatment arm.

Secondary efficacy analyses

The distribution of cessation of symptoms will be estimated using the Kaplan-Meier method, and Kaplan-Meier curves will be presented for each treatment arm. Time to cessation of symptoms at the end of the study period along with 95% confidence intervals will be presented for each treatment arm. The hazard ratio for cessation of symptoms will be estimated, along with its 95% confidence intervals, from a Cox proportional hazards model. Time to cessation of symptoms will be determined by analysis of daily questionnaires. Resolution of symptoms requires that symptoms are mild or absent for at least 24 hours.

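### Diarrhoea is both a named favipiravir adverse event and a scored COVID-19 symptom, and the plan has no rule for which it is; drug-caused GI events can be missed in coded safety tables and counted as symptom onset

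*Combined protocol and SAP*

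**What the plan says.** Section 2.3 states that transient uric acid elevation and "mild to moderate diarrhea are the two most common AEs known to occur with favipiravir". The same section adds that in double-blind studies "the adverse event profile of favipiravir and placebo were similar with the exception of elevations of uric acid".

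The efficacy diary (synopsis, study measurements; section 8.1) includes "GI symptoms including nausea, vomiting, and/or diarrhea" as one item. The section 8.1 list also has abdominal pain; the synopsis diary list does not. Three secondary endpoints in the synopsis draw on symptoms:

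- Endpoint 2, in its second part, is development of COVID-19 symptoms in asymptomatic subjects.
- Endpoint 5 is time to cessation of symptoms, defined as "absence of symptoms for at least 24 hours for those with mild symptoms". Section 9.6 defines it differently: "Resolution of symptoms requires that symptoms are mild or absent for at least 24 hours".
- Endpoint 6 is "Absence of development of any symptoms among those enrolled with asymptomatic infection".

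On safety, section 8.4.2 lists "Clinical events related to the progression of COVID-19" among things that are not AEs. Section 9.7 limits MedDRA coding to the terms used to "identify AEs other than symptoms of COVID-19 will be fully described and coded", and summarises TEAEs by MedDRA organ class and preferred term. Section 8.4.3 requires new or worsened events after dosing to be recorded and assessed for relationship to study drug.

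**The concern.** The same loose stool can be a drug effect or a disease symptom, and no section says how to classify it. The site is blinded and the participant has confirmed infection, so COVID-19 is always an available explanation. Two secondary objectives are exposed. For safety and tolerability (objective 2), GI events attributed to the disease can fail to reach the coded TEAE tables. For symptoms (part of objective 1), a drug-caused GI event can be scored as a failure on a symptom endpoint. If favipiravir does cause more GI events than placebo, the first effect makes it look better tolerated than it is, and the second makes it look less effective on symptoms. Section 2.7 expects this trial to help define the safety profile and to support a larger pivotal study.

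**Working it through.** The plan gives no GI rate and no power for AE or symptom endpoints, so there is no stated figure to reproduce. The check is a reading of the rules together, followed by illustrations on assumed rates.

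**Following one case.** An asymptomatic enrollee has diarrhoea on Day 3.

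1. *Efficacy.* Endpoint 6 fails on any symptom, with no severity threshold or attribution rule. The asymptomatic part of endpoint 2 records the same event. In symptomatic subjects endpoint 2 needs respiratory distress or symptoms requiring hospitalization, so ordinary diarrhoea does not count there.
2. *Recording.* Section 8.4.3 calls for the event to be recorded. Section 8.4.2 allows a site that sees it as COVID-19 progression not to treat it as an AE.
3. *Coding.* If it is recorded, the section 9.7 limit applies at coding, so an event regarded as a COVID-19 symptom need not reach the preferred-term tables.
4. *Relatedness.* The section 8.4.3 definition of related requires that the subject's clinical state cannot explain the event. With confirmed infection that is hard to meet, so the treatment-related rows can lose it too.
5. *Backstop.* The safety sources in the synopsis and section 8.4 do not include the symptom diary, and section 9.7 plans no diary table by arm.

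**Endpoint 5.** Under the synopsis definition (absence), mild diarrhoea delays cessation. Under section 9.6 (mild or absent) it does not; only moderate or worse diarrhoea would.

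**Illustration A, safety tables.** Let the true rates be p0 on placebo and p1 = p0 + d on favipiravir, and let a fraction q of GI events be attributed to COVID-19. Blinding suggests the same q in both arms. The visible rates are p0(1−q) and p1(1−q), so the visible difference is d(1−q). Power is the normal approximation for two proportions, two-sided 0.05, with the planned 90 per arm.

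| Assumed true rates | Visible rates, q = 0.5 | Power, q = 0 | Power, q = 0.5 |
|---|---|---|---|
| 10% vs 20% | 5% vs 10% | 0.47 | 0.25 |
| 10% vs 25% | 5% vs 12.5% | 0.76 | 0.43 |

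Over p0 of 5%, 10% and 20% and d of 5, 10 and 15 points, power runs from 0.12 to 0.87 with q = 0, and from 0.08 to 0.55 with q = 0.5.

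**Illustration B, endpoint 6.** Assume 40% of placebo and t = 30% of favipiravir asymptomatic enrollees truly develop COVID-19 symptoms, and that the drug causes GI symptoms in a fraction x of the remainder. The observed favipiravir rate is t + (1−t)x.

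- x = 0.05: 0.30 + 0.70 × 0.05 = 0.335; difference from 0.40 is 6.5 points.
- x = 0.10: 0.30 + 0.70 × 0.10 = 0.370; difference is 3 points.

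The true difference is 10 points.

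**Illustration C, endpoint 5 under the synopsis definition only.** This is a large simulation (200,000 per arm) with exponential symptom times, daily assessment and 28 days, in which drug-caused GI symptoms last through Day 10 in 5% to 15% of the favipiravir arm. The Cox estimates are:

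| True HR | Control median | No drug GI | 5% to 15% drug GI |
|---|---|---|---|
| 1.5 | 7 days | 1.47 | 1.42 to 1.33 |
| 1.5 | 10 days | 1.48 | 1.44 to 1.40 |
| 1.0 | 7 days | 1.00 | 0.98 to 0.94 |
| 1.0 | 10 days | 1.00 | 0.99 to 0.96 |

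Under the section 9.6 definition, mild diarrhoea would cause none of this attenuation.

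**The case against.** A reader might infer that the plan leaves diarrhoea out of AE coding altogether. It does not say so. Section 8.4.3 requires new and worsened events to be recorded, and lists underlying disease as a reason to call a recorded AE unrelated, not as a reason to leave it unrecorded. Staff query subjects about AEs (8.4.1), and the opening sentence of section 9.7 tabulates AEs by type and arm without the COVID-19 limit. Loss depends on how a site or coder attributes the event, and blinded attribution dilutes a difference rather than erasing it. This stands, and it is why the point is worded as what can happen.

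A reader might also infer that bias against favipiravir is established. It is not. Section 2.3 reports a placebo-like profile apart from uric acid, so the documents do not show an excess of diarrhoea over placebo. Nor does the 10-day course prove one: section 2.3 describes a longer open-label Ebola regimen as apparently well tolerated, and section 2.6 cites safety data for 10 days and beyond. What can be said is conditional: if there is an excess, it falls in the active arm.

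It is tempting to count three affected endpoints. The relevant part of endpoint 2 mirrors endpoint 6, and endpoint 5 is open to mild diarrhoea only under one of its two definitions.

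Counting all symptoms whatever their cause is a legitimate measure of patient burden, so removing GI items should not replace the main analysis. Finally, section 9 defers full details to a formal SAP and section 3.2 refers to a manual of procedures; a classification rule could be placed there, but the text under review contains none.

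**Conclusion.** The concern holds in a conditional form. The rules as written allow drug-caused GI events that are attributed to COVID-19 to be missing from the coded TEAE tables, and to count as symptom development in asymptomatic enrollees. For endpoint 5, mild diarrhoea matters only if the synopsis definition governs, and that conflict with section 9.6 needs resolving in any case.

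The size is unknown. Every rate in the illustrations is assumed; they show the direction of the effect and how much it could matter, not what will happen. The effect may be small. The primary endpoint, RT-PCR shedding, is untouched. The change is worth making because it is cheap and because, without it, the coded tables are a weak basis for saying whether GI tolerability differs between arms. A reader should not conclude that the safety results are invalid or that symptom efficacy is shown to be biased.

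**What to change.** 1. In sections 8.4.2 and 9.7, state that GI events that are new or worse than the Day 1 baseline after the first dose are recorded and coded as TEAEs whatever their attribution to COVID-19.
2. In section 9.7, tabulate the diary GI item by arm in the safety population: nausea, vomiting and diarrhoea as the single item the diary holds, plus abdominal pain where the diary collects it.
3. In section 9.6, keep the all-symptom analyses and add a sensitivity analysis of endpoints 5 and 6, and of the asymptomatic part of endpoint 2, without the GI items. Report it beside the main result.
4. Use one definition of symptom cessation in the synopsis and section 9.6, and make the two diary lists agree on abdominal pain.

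The cost is protocol and SAP wording, one extra safety table, one extra run of each symptom analysis, and some additional AE recording and coding. The diary and the Day 1 symptom survey (section 7.1) should supply most of the data, but the survey form is not shown and the diary combines nausea, vomiting and diarrhoea, so diarrhoea alone may not be separable from it. There are two downsides: the safety table will include some disease-related events in both arms, and the sensitivity analysis will drop genuine COVID-19 GI symptoms.
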